datasets, depending on the number of imputed monotone datasets that are required. The seed or number of imputed datasets may be changed after unblinding in case of any issues with the imputation process, and it will be documented in the CSR if any change is required.

3. For each completed dataset, compute the necessary derived variables. The dichotomous success rate (clear or almost clear) will be derived. The results obtained will be analyzed using the CMH analysis for each of the complete analysis data sets stratified by baseline IGA score and site. The results will be combined into one multiple imputation inference (odds ratio, associated CI, and *P* value) using PROC MIANALYZE as illustrated below (Ratitch 2013).

This approach to imputation should be superior to other strategies such as carrying forward the last available observation, which may yield unrealistic imputed values. Also, the use of multiple imputation avoids the problem of artificially increasing power through data imputation associated with single-imputation methods because it accounts for the uncertainty associated with the imputation. Other missing data will not be imputed, with the exception of incomplete dates as described in Section 6.1.8. For responder analyses, missing data will be treated as a nonresponse with the exception of IGA. Only observed data will be summarized using descriptive statistics.

The SAS pseudo code for the multiple imputation process is listed below:

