- **HECSI Total Score** = sum of HECSI Fingertips, Fingers (except tips), Palm of Hands, Back of Hands, and Wrists subscores. The range for the HECSI Total score is 0 to 360. Lower scores indicate better outcomes.
- **HECSI-75** = achievement of a 75% reduction in HECSI total score from baseline.
- **Average Weekly Pain NRS Score** = Pain NRS scores will be assigned to a particular study week based on the study week window, as shown in [Section 6.1.5.2](#). If 2 or more observations are present for a single day, those observations will be averaged into a single daily value before calculating the average weekly score. The average of the reported (non-missing) Pain NRS scores assigned to each study week will be calculated. If at least 1 Pain NRS score is present in this time period, the average weekly Pain NRS score will be calculated; otherwise the average weekly score will be missing for that week.
- **Pain NRS 4-point Reduction** = achievement of a 4-point reduction in Pain NRS score at each study week compared to baseline, calculated only for subjects with a Pain NRS score of  $\geq 4$  at baseline (PNRS4 population).

- **QOLHEQ Symptoms Subscore** = sum of QOLHEQ questions 1, 6, 9, 11, 20, 23, and 28. Questions 1, 6, 9, 11, 20, and 23 are scored such that never = 0, rarely = 1, sometimes = 2, often = 3, and all the time = 4; question 28 is scored such that never = 0, rarely = 1, sometimes = 1, often = 2, and all the time = 3. The range for QOLHEQ Symptoms subscore is 0 to 27, where lower scores indicate better outcomes. If 1 question has a missing result, set the missing result to 0 before summing; if more than 1 question is missing, then the QOLHEQ Symptoms subscore cannot be calculated.
- **QOLHEQ Emotions Subscore** = sum of QOLHEQ questions 5, 8, 10, 16, 19, 21, 27, and 30. Questions 5, 8, 16, 19, 21, 27, and 30 are scored such that never = 0, rarely = 1, sometimes = 2, often = 3, and all the time = 4; question 10 is scored such that never = 0, rarely = 1, sometimes = 1, often = 2, and all the time = 3. The range for QOLHEQ Emotions subscore is 0 to 31, where lower scores indicate better outcomes. If 1 question has a missing result, set the missing result to 0 before summing; if more than 1 question is missing, then the QOLHEQ Emotions subscore cannot be calculated.

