- **QOLHEQ Limitations in Functioning Subscore** = sum of QOLHEQ questions 2, 3, 12, 14, 15, 17, 25, and 29. All questions are scored such that never = 0, rarely = 1, sometimes = 2, often = 3, and all the time = 4. The range for QOLHEQ Limitations in Functioning subscore is 0 to 32, where lower scores indicate better outcomes. If 1 question has a missing result, set the missing result to 0 before summing; if more than 1 question is missing, then the QOLHEQ Limitations in Functioning subscore cannot be calculated.
- **QOLHEQ Treatment and Prevention Subscore** = sum of QOLHEQ questions 4, 7, 13, 18, 22, 24, and 26. Questions 7, 13, 18, 22, 24, and 26 are scored such that never = 0, rarely = 1, sometimes = 2, often = 3, and all the time = 4; question 4 is scored such that never = 0, rarely = 1, sometimes = 1, often = 2, and all the time = 3. The range for QOLHEQ Treatment and Prevention subscore is 0 to 27, where lower scores indicate better outcomes. If 1 question has a missing result, set the missing result to 0 before summing; if more than 1 question is missing, then the QOLHEQ Treatment and Prevention subscore cannot be calculated.
- **QOLHEQ Total Score** = sum of all 30 QOLHEQ questions. Questions 4, 10, and 28 are scored such that never = 0, rarely = 1, sometimes = 1, often = 2, and all the time = 3; otherwise, questions are scored such that never = 0, rarely = 1, sometimes = 2, often = 3, and all the time = 4. The range for QOLHEQ Total score is 0 to 117, where lower scores indicate better outcomes. If 1 to 3 questions have a missing result, set the missing result to 0 before summing; if more than 3 questions are missing, then the QOLHEQ Total score cannot be calculated.
- **Total Hand % BSA Affected by Disease** = sum of % BSA affected by disease from the following hand areas: left palmar, left dorsal, right palmar, and right dorsal. All 4 hand areas must have a result for the total hand % BSA affected by disease to be calculated.
- **Compliance** = number of applications divided by the expected number of investigational product (IP) applications for each subject. Compliance will be calculated using drug accountability data over the entire treatment period for each subject, up to treatment completion or discontinuation.

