- **Number of Expected IP Applications (BID dosing)** = 170 (Cohort 2 BID) for subjects who complete the study or number of days between first and last application of IP, derived as  $2 * (\text{last treatment date} - \text{first treatment date} + 1)$ , for subjects who discontinue early from the study.
- **Number of Expected IP Applications (QD dosing)** = 30 (Cohort 1) or 85 (Cohort 2 QD) for subjects who complete the study or number of days between first and last application of IP, derived as  $(\text{last treatment date} - \text{first treatment date} + 1)$ , for subjects who discontinue early from the study.
- **Number of IP Applications** = number of expected IP applications – missed IP applications as collected in the electronic case report form (eCRF).
- **Weight of IP (g)** = returned tube weight – dispensed tube weight.
- **Body Mass Index (BMI) ( $\text{kg}/\text{m}^2$ )** =  $[\text{weight (kg)} / \text{height (cm)} / \text{height (cm)}] \times 10,000$ .
- **Change from Baseline** = value at current time point – value at baseline.
- **Treatment Emergent AE (TEAE)** = any AE with an onset date/time after the first application of IP. If time is unavailable, any AE occurring on or after the date of first application of IP will be considered treatment emergent.
- **Completion of Study** = Completion of the primary efficacy assessment (IGA) at Week 12. This may differ than what was recorded in the eCRF.

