Note: Subjects are summarized by planned treatment. The construct Health Related Quality of Life (HRQOL) includes all impairments or limiting conditions caused by the health state of an individual. The QOLHEQ is a disease specific instrument, thereby only assessing impairments caused by hand eczema. It consists of 30 items which can be summarized according to these four domains: Impairments because of (1) symptoms (range 0 to 27), (2) emotions (range 0 to 31), (3) limitations in functioning (range 0 to 32), or (4) because of treatment and prevention (range 0 to 27); the total score is the sum of the subscores and has a range of 0 to 117. Lower scores indicate better outcomes. Baseline is the last non-missing measurement taken on or before the day of first application of study drug. Change from baseline is calculated as result – baseline result. Percent change from baseline is calculated as (change from baseline/baseline)\*100.  
Reference Listing: 16.2.6.5

Table 14.2.2.4.2

Cohort 2, Pooled Treatments: Summary and Change and Percent Change from Baseline in Quality of Life in Hand Eczema Questionnaire (QOLHEQ) Subscores and Total Score  
by Study Visit  
ITT Population

(Same shell as Table 14.2.2.2.2; parameters include the following: Symptoms Subscore, Emotions Subscore, Limitations in Functioning Subscore, Treatment and Prevention Subscore, and Total Score; use the below footnotes)

Abbreviations: QOLHEQ = Quality of Life in Hand Eczema Questionnaire; SD = standard deviation.

Note: Subjects are summarized by planned treatment. The construct Health Related Quality of Life (HRQOL) includes all impairments or limiting conditions caused by the health state of an individual. The QOLHEQ is a disease specific instrument, thereby only assessing impairments caused by hand eczema. It consists of 30 items which can be summarized according to these four domains: Impairments because of (1) symptoms (range 0 to 27), (2) emotions (range 0 to 31), (3) limitations in functioning (range 0 to 32), or (4) because of treatment and prevention (range 0 to 27); the total score is the sum of the subscores and has a range of 0 to 117. Lower scores indicate better outcomes. Baseline is the last non-missing measurement taken on or before the day of first application of study drug. Change from baseline is calculated as result – baseline result. Percent change from baseline is calculated as (change from baseline/baseline)\*100.  
Reference Listing: 16.2.6.5

Table 14.2.2.4.3

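### Blank QOLHEQ items are scored 0, the best answer, so blanks at only one visit shift that subject's change from baseline by up to 12 of 117 points

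*SAP*

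**What the plan says.** SAP 6.1.7 builds the QOLHEQ total from 30 items. Three items use a collapsed code: "Questions 4, 10, and 28 are scored such that never = 0, rarely = 1, sometimes = 1, often = 2", with 3 as the top value. For the other 27, "otherwise, questions are scored such that never = 0, rarely = 1, sometimes = 2, often = 3, and all the time = 4". On direction, "The range for QOLHEQ Total score is 0 to 117, where lower scores indicate better outcomes".

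For blanks, the total rule is "If 1 to 3 questions have a missing result, set the missing result to 0 before summing"; with more than three blanks no total is computed. Each of the four subscores has its own rule: "If 1 question has a missing result, set the missing result to 0 before summing"; with more than one blank there is no subscore. Change from baseline is "value at current time point – value at baseline", so a negative change is an improvement.

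SAP 6.1.4, after setting out the IGA imputation, states: "Other missing data will not be imputed, with the exception of incomplete dates". SAP 8.2.5 describes the QOLHEQ analyses as using nonimputed data only. Neither section mentions blank items.

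The footnotes to Tables 14.2.2.4.1 to 14.2.2.4.4 describe the total differently from 6.1.7: "the total score is the sum of the subscores and has a range of 0 to 117".

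**The concern.** A skipped item is given the value that stands for no impairment. A subject whose quality of life has not moved, but who leaves items blank at a later visit, is recorded as improved. The same blanks at baseline alone record a worsening.

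The rest of 6.1.7 goes the other way. A missing HECSI component leaves the subscore uncalculated unless the affected area is 0, and total hand BSA needs all four areas. Only QOLHEQ receives a best-case fill.

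Blanks are plausible. The form in Protocol Appendix 1 has 30 items, five frequency options and no option for an item that does not apply, although it asks about the job, the partner and self-paid treatment costs. SAP 6.2 also allows remote completion.

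At stake are change and percent change in QOLHEQ. These are secondary endpoints analysed by ANCOVA, and the table shells also test each arm's change against zero.

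**Working it through.** **Inputs.** Item codes, domain lists, blank limits and the definition of change are all from SAP 6.1.7. The documents give no rate of blank items.

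**Reproducing the stated ranges.** The four domain lists use questions 1 to 30 exactly once.
- Symptoms: 6×4 + 3 = 27
- Emotions: 7×4 + 3 = 31
- Functioning: 8×4 = 32
- Treatment and prevention: 6×4 + 3 = 27
- Total: 27 + 31 + 32 + 27 = 117, and directly 27×4 + 3×3 = 117

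These agree with the SAP.

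**Largest shift.** Three blank 4-point items that would have been *all the time* lose 3×4 = 12 points, and 12/117 = 10.3% of the range. If the blanks are questions 4, 10 and 28, the loss is 3×3 = 9. One blank in a subscore loses at most 4.

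**Literal records.** Take a subject who gives the same answer to every item at both visits, with a complete baseline and three 4-point items blank later. The last column is the answered sum × 117/105, since the answered items can reach 117 − 12 = 105.

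| Uniform answer | Baseline total | Later total, blanks = 0 | Change | Later total, pro-rated (change) |
|---|---|---|---|---|
| *rarely* | 27×1 + 3×1 = 30 | 27 | −3 (−10.0%) | 30.09 (+0.09) |
| *sometimes* | 27×2 + 3×1 = 57 | 51 | −6 (−10.5%) | 56.83 (−0.17) |
| *often* | 27×3 + 3×2 = 87 | 78 | −9 (−10.3%) | 86.91 (−0.09) |
| *all the time* | 27×4 + 3×3 = 117 | 105 | −12 (−10.3%) | 117.00 (0) |

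The true change is 0 in every row. With the same blanks at baseline only, the changes become +3, +6, +9 and +12. With the same items blank at both visits, the zeros cancel (for *often*, 78 against 78).

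For the Symptoms subscore, uniform *often* gives 6×3 + 2 = 20. One blank 4-point item gives 17, a change of −3 (−15%).

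**Effect on a mean.** As an assumption, let a share f of an arm's Week 12 forms have three such blanks, from *often* responders with complete baselines. The arm's mean change is overstated by 9f: 0.45 points at f = 5% and 1.8 at f = 20%. If f and the points lost are the same in active and vehicle, the unadjusted difference between arms moves by 9f − 9f = 0. If f differed by 5 percentage points, it would move by 9×0.05 = 0.45.

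**Total and subscore rules.** Two blanks in one domain make that subscore missing, yet the total is computed with both as 0. One blank in each of four domains leaves all four subscores computable, yet four blanks exceed the limit for the total. The item-sum definition in 6.1.7 and the subscore-sum description in the footnotes therefore agree on complete forms but can part on incomplete ones.

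**The case against.** **The contrast.** A reader might infer that blank items are turned into treatment benefit. The documents do not support that. The rule is the same in every arm, Cohort 2 is blinded to product (SAP 3.6), and the efficacy comparison is active against vehicle. Bias there needs blank rates, or the severity of skipped items, to differ by arm, and nothing in the documents points to such a difference. This objection stands and limits the point to individual records and within-arm changes.

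**Items that do not apply.** A subject without a job would probably leave the job item blank at every visit, so the zeros largely cancel. For that subject 0 is arguably the right value, and pro-rating would assign an *often* responder about 3 points of impairment on that item. This also stands, as a cost of the fix. It does not rescue the rule, which cannot tell an inapplicable item from a skipped one.

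**A scoring convention, not imputation.** Section 6.1.7 is a specific derivation, and 6.1.8 makes statistics-derived questionnaire scores the ones used in analysis, so a programmer has a clear instruction. The SAP also sets values elsewhere: 8.3 fills in 0 mm for the nail measure while calling its data nonimputed, and 9.1 treats missing severity as severe. The nonimputed label may therefore mean only that multiple imputation was not used. That softens the conflict, but 6.1.4 lists its exceptions and this is not among them. The collapsed coding and the blank limits may come from the instrument, but the SAP does not say so, and its reference list has no QOLHEQ scoring source.

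**Stakes.** SAP 4.1 makes P values informational for endpoints other than the primary IGA endpoint and the HECSI changes. That stands.

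**Conclusion.** The point holds as a minor one. The zero rule gives a wrong change score for any subject whose blanks on applicable items, where some impairment would have been reported, differ between baseline and a later visit. The error is at most 12 of 117 points for the total and 4 points for a subscore, and about 10% of the baseline total for a uniform responder with three 4-point blanks. Its direction depends on which visit has the blanks. The maximum rests on three 4-point items whose true answer was *all the time*; the 0.45 to 1.8 point shift in an arm mean rests on an assumed share of forms and an assumed answer pattern.

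No bias in the active-vehicle contrast has been shown. The conflict with 6.1.4 and 8.2.5, and the mismatch between 6.1.7 and the table footnotes, are on the page whatever the blank rate turns out to be.

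**What to change.** In SAP 6.1.7, replace zero-filling by pro-rating to the maximum attainable score:
- Subscore = sum of answered items × (domain maximum / maximum of the answered items), with at most 1 blank.
- Total = sum of answered items × (117 / maximum of the answered items), with at most 3 blanks.

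This keeps the current limits and cannot exceed the stated ranges. With question 28 blank and all other Symptoms items at *all the time*, it gives 24 × 27/24 = 27. Filling with the domain's mean item would give 6×4 + 4 = 28, above the range of 27.

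If zero-scoring is the instrument's convention, keep it as the main score, cite the source, and report the pro-rated score as a sensitivity analysis.

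In either case:
- Name the item-level exception in 6.1.4 and 8.2.5.
- Reword the footnotes of Tables 14.2.2.4.1 to 14.2.2.4.4 so that the total is defined over the 30 items, as in 6.1.7. Defining it through the subscores would lose totals from forms with two blanks in one domain.

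A count of blank items by arm and visit would show whether the contrast is exposed at all.

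The cost is SAP wording, a few lines of code and one extra table. The drawback is that pro-rating may assign impairment to items that truly do not apply.
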